7.2. Secondary Objectives

1. Evaluate the proportion of patients eligible for sequence analysis with VOC and VUI on the earliest possible sample including baseline
2. Evaluate the proportion of patients with undetectable virus at Day 7, 14 and 28 (+/-2 days) by RT-PCR
3. Evaluate the proportion of patients with key clinical outcomes (hospital admission, requirement for respiratory support, ICU admission and death) through Day 28 post sotrovimab administration
4. Describe AA (detected at >5% allelic frequency) changes in the SARS-CoV-2 spike protein in samples collected at Day 7, 14 and 28 (+/-2 days) compared to baseline following sotrovimab administration for samples with viral loads above the threshold of the sequencing assay
5. Describe AA changes in the consensus sequence (>50%) of SARS-CoV-2 spike protein in samples collected at Day 7, 14 and 28 (+/-2 days) compared to baseline following sotrovimab administration for samples with viral loads below the threshold for detection of AA changes at >5% allelic frequency but with sufficient levels to generate consensus sequencing data

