All the raw data (FASTA/ FASTQ/BAM/VCF files) will be directly uploaded to GSK's SFTP in near-real time by UCL and SYNH will not be involved in this process.

This document is confidential.

6. Endpoints

Primary Endpoints
1. Proportion of patients eligible for sequence analysis that have any Amino Acid change from baseline in the epitope of sotrovimab binding in samples collected at Day 7, 14 and 28 (+/-2 days) (Primary Objective 1)
2. Proportion of patients eligible for sequence analysis that have any Amino Acid change from baseline in the spike protein in samples collected at Day 7, 14 and 28 (+/-2 days) (Primary Objective 2)
Secondary Endpoints
3. Proportion of patients eligible for sequence analysis with SARS CoV-2 VOC or VUI on the earliest possible sample (Secondary Objective 1) • Variant identification, pango lineage and AA changes in VOC and VUI in addition to their defining mutations will be reported
4. Proportion of patients with undetectable virus at Day 7, 14 and 28 (+/-2 days) (Secondary Objective 2)
5. Clinical outcomes through Day 28 post sotrovimab treatment (Secondary Objective 3): • Proportion of all cause hospital admissions and related to COVID-19 • Proportion of patients requiring new or increased oxygen support (supplemental oxygen [not high flow], non-invasive ventilation or high-flow, invasive mechanical ventilation or Extracorporeal membrane oxygenation [ECMO]) • Proportion of all cause ICU admissions • Proportion of all cause deaths and COVID-19 related deaths
6. AA (detected at >5% allelic frequency) changes in the SARS-CoV-2 spike protein in samples collected at Day 7, 14 and 28 (+/-2 days) compared to baseline following sotrovimab administration for samples with viral loads above the threshold of the sequencing assay (Secondary Objective 4)
7. AA changes in the SARS-CoV-2 spike consensus sequences from baseline in samples where viral load is insufficient for >5% allelic frequency analysis but sufficient to generate consensus level sequencing data (Secondary Objective 5)
Exploratory Endpoints
1. Describe viral characteristics (e.g. viral load, VOC/VUI, AA changes) in patients who subsequently require hospital admission or die due to COVID-19 post sotrovimab treatment.

This document is confidential.

The following separate tables will be presented to support the above viral characteristics endpoint:

- Please refer Table 1.26 for analysis on VOC/VUI for hospitalized patients.

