8.2 Key Definitions

End of Study (EOS)

The EOS is defined as the date the last participant completes the last visit as shown in the Schedule of Activities in [Section 4.8](#).

Study day

Event date can be adverse events, labs, or any other assessments during the study.

If the event date \geq date of first dose of sotrovimab, study day = event date – date of first dose of sotrovimab + 1.

If the event date $<$ date of first dose of sotrovimab, study day = event date – date of first dose of sotrovimab.

Baseline Value

Baseline value will be defined as the last non-missing value recorded prior to sotrovimab administration or as close as possible to the end of sotrovimab infusion.

Retrospective collection of baseline data with the patient or directly with patient HCP will be conducted when not possible at Day 0. In all cases baseline is defined to be Day 0.

Change from Baseline (CFB)

CFB = Post-baseline value – Value at baseline

Treatment Emergent

Treatment emergent amino acid substitutions include subjects where baseline and post-baseline records exist.

Treatment emergence for consensus will include baseline records of allelic frequency $>5\%$ and post-baseline $>50\%$ as thresholds, whereas treatment emergence for minority will include baseline records of allelic frequency $>5\%$ and post-baseline $>5\%$ as thresholds.

Consensus sequence is defined as allelic frequency $>50\%$ and minority species with allelic frequency $>5\%$.

Lower Limit of Detection (LLOD)

LLOD of the assay is defined as 453 copies/mL (equivalent to Ct=38).

Lower Limit of Quantification (LLOQ)

LLOQ of the assay is defined as 1570 copies/mL (equivalent to Ct=36.18).

Viral load Negatives

The threshold to declare a viral load negative is the LLOD.

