9.5 Prior and Concomitant Medication

Prior and concomitant medications will be coded by the Anatomical Therapeutic Chemical (ATC) classification system according to the World Health Organization Drug Dictionary (WHO-DD). Medications will be classified as concomitant or prior and summarized by ATC class (level 2, therapeutic subgroup) and preferred drug name for all subjects in the safety population.

Prior medication is defined as any medication taken before the date of the first dose of study treatment. Concomitant medication is defined as any medication taken on or after the date of the first dose of study treatment.

Concomitant medication will be recorded, including the medication name, daily dose, unit, regimen, administration route, reason for administration (text field) and medication start and end dates or ongoing. All prior and concomitant medications will be listed, with a flag identifying prior medications, for all subjects in the Safety population.

The summary tables will show the frequency and percentage of subjects in each group with at least one usage of medication on the sub-class level within each ATC class sorted alphabetically.

10. Efficacy

Treatment Emergent Amino acid Substitutions/Amino acid Change from Baseline is defined as any amino acid substitutions detected at post-baseline visits compared to baseline sequence.

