10.1 Primary Efficacy Endpoint and Analysis

Primary efficacy analyses will be conducted for the safety populations.

The primary endpoints in this study are

- Proportion of patients eligible for sequence analysis that have any AA change from baseline in the epitope of sotrovimab binding.

The proportion of subjects with epitope amino acid change from baseline will be summarized showing the counts and percentages of patients in each epitope substitution change by post-baseline visits (Day 7, 14 and 28 (+/-2 days)) and overall and will be presented separately for Minority species (>5% allelic frequency) as well as consensus sequence (>50% allelic frequency).

Proportion of patients with epitope substitution change by VOC/VUI for Consensus Sequence (Allelic frequency >50%) and for Minority species (>5% allelic frequency) was also presented by visit for interim analysis reporting, but will not be included in the final analysis.

- Proportion of patients eligible for sequence analysis that have any AA change from baseline in the spike.

The proportion of subjects with spike amino acid change from baseline will be summarized showing the counts and percentages of patients in each spike substitution change by post-baseline visits (Day 7, 14 and 28 (+/-2 days)) and overall and will be presented separately for Minority species (>5% allelic frequency) as well as consensus sequence (>50% allelic frequency).

This document is confidential.

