Table	1.3	Summary of Proportion of Amino Acid Substitutions in the Spike protein for Any Substitutions – Consensus Sequence (Allelic frequency >50%)	Safety	Interim, Final
Table	1.4	Summary of Proportion of Amino Acid Substitutions in Epitope for Any Substitutions – Consensus Sequence (Allelic frequency >50%)	Safety	Interim, Final
Table	1.5	Summary of Proportion of Amino Acid Substitutions in the Spike protein for Any Substitutions – Minority species (Allelic frequency >5%)	Safety	Interim, Final
Table	1.6	Summary of Proportion of Amino Acid Substitutions in Epitope for Any Substitutions – Minority species (Allelic frequency >5%)	Safety	Interim, Final
Table	1.7	Summary of Proportion of Amino Acid Substitutions at Baseline and Post-Baseline in Spike protein – Consensus Sequence (Allelic frequency >50%)	Safety	Interim, Final
Table	1.8	Summary of Proportion of Amino Acid Substitutions at Baseline and Post-Baseline in Epitope – Consensus Sequence (Allelic frequency >50%)	Safety	Interim, Final
Table	1.9	Summary of Proportion of Amino Acid Substitutions at Baseline and Post-Baseline in Spike protein – Minority species (Allelic frequency >5%)	Safety	Interim, Final

This document is confidential.

Table	1.10	Summary of Proportion of Amino Acid Substitutions at Baseline and Post-Baseline in Epitope – Minority species (Allelic frequency >5%)	Safety	Interim, Final
Table	1.11	Summary of Proportion of Treatment-emergent Amino Acid Substitutions in the Spike Protein for Any Substitutions – Consensus Sequence (Allelic frequency >50%)	Safety	Interim, Final
Table	1.12	Summary of Proportion of Treatment-emergent Amino Acid Substitutions in the Epitope for Any Substitutions – Consensus Sequence (Allelic frequency >50%)	Safety	Interim, Final
Table	1.13	Summary of Proportion of Treatment-emergent Amino Acid Substitutions in the Spike Protein for Any Substitutions – Minority species (Allelic frequency >5%)	Safety	Interim, Final
Table	1.14	Summary of Proportion of Treatment-emergent Amino Acid Substitutions in the Epitope for Any Substitutions – Minority species (Allelic frequency >5%)	Safety	Interim, Final
Table	1.15	Summary of Proportion of Subjects with a Variant of Concern/Under Investigation (VOC/VUI)	Safety	Interim, Final
Table	1.161	Summary of Absolute Viral Load (log 10 copies/mL) as measured by qRT-PCR from Nasal/oropharyngeal swabs	Safety	Interim, Final

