Table	1.46	Summary of Proportion of Subjects with Amino Acid Substitutions in the Spike protein for Any Substitutions – Minority species (Allelic frequency >5%)	Safety	Final

This document is confidential.

Table	1.47	Summary of Proportion of Subjects with Treatment-emergent Amino Acid Substitutions in the Spike protein for Any Substitutions– Consensus Sequence (Allelic frequency >50%)	Safety	Final
Table	1.48	Summary of Proportion of Subjects with Treatment-emergent Amino Acid Substitutions in the Spike protein for Any Substitutions– Minority species (Allelic frequency >5%)	Safety	Final
Table	1.49	Summary of Absolute Viral Load (log 10 copies/mL) as measured by qRT-PCR from Nasal/oropharyngeal swabs in subjects with clinical outcomes	Safety	Final
Table	1.50	Proportion of subjects with undetectable viral load as measured by qRT-PCR from Nasal/oropharyngeal swab through Day 28 in subjects with clinical outcomes	Safety	Final
Table	1.51	Summary of Proportion of Amino Acid Substitutions at Baseline and Post-Baseline in Spike protein - Consensus Sequence (Allelic frequency >5%) in subjects with clinical outcomes	Safety	Final

15. Index of Figures

Figures	List of Interim and Final Reports	Population	Analysis
1.1	Mean Change from Baseline of Viral Load Log10 copies/mL	Virology	Interim, Final
1.2	Median Viral Load Log10 copies/mL by VOC/VUI	Safety	Interim, Final
1.3	Median viral load Log10 copies/mL over time of Epitope Substitution by Residue	Safety	Interim, Final
1.4	Individual subjects profile plot of viral load Log10 copies/mL by VOC/VUI	Safety	Interim, Final
1.5	Kaplan-Meier Plot for All-Cause Hospitalization by VOC/VUI subvariants –	Safety	Interim

This document is confidential.

16. Index of Listings

Listings		List of Interim and Final Reports	Population	Analysis
Listing	1.1	Subject Disposition	Screened	Interim, Final
Listing	1.2	Demographics and Baseline Characteristics	Safety	Interim, Final
Listing	1.3	Listing of all Baseline and Post-baseline Spike protein Amino Acid Substitutions – Minority species (Allelic frequency >5%)	Safety	Interim, Final
Listing	1.4	Listing of all Baseline and Post-baseline Spike protein Amino Acid Substitutions – Consensus sequence (Allelic frequency >50%)	Safety	Interim, Final
Listing	1.5	Listing of all Baseline and Post-baseline Epitope Amino Acid Substitutions – Minority species (Allelic frequency >5%)	Safety	Interim, Final

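### SAP 8.2 leaves out the condition that makes a substitution treatment-emergent, and on the likely intended reading a rise from >5-50% at baseline to >50% after baseline is in no emergent count

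*SAP*

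**What the plan says.** **Endpoint.** SAP section 6 defines the first primary endpoint as the proportion of sequence-eligible patients "that have any Amino Acid change from baseline in the epitope of sotrovimab binding". The second is the same for the whole spike protein. SAP 10.1 reports both at two levels, minority species (>5%) and consensus (>50%).

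**Definition, first place.** SAP 8.2 (Treatment Emergent) requires baseline and post-baseline records. It then says "Treatment emergence for consensus will include baseline records of allelic frequency" >5% and post-baseline >50%. For minority species both values are >5%. It calls these values thresholds.

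**Definition, second place.** The opening of SAP section 10 treats treatment emergence and change from baseline as one concept: "any amino acid substitutions detected at post-baseline visits compared to baseline sequence". It gives no frequency, and it does not say whether the baseline sequence means the >5% calls or the >50% calls.

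**Outputs.** The emergent results are in Tables 1.11-1.14, for example "Summary of Proportion of Treatment-emergent Amino Acid Substitutions in the Epitope for Any Substitutions" (1.12 and 1.14), and in Tables 1.47-1.48, "Summary of Proportion of Subjects with Treatment-emergent Amino Acid Substitutions in the Spike protein for Any Substitutions". Tables 1.7-1.10 (for epitope, "Summary of Proportion of Amino Acid Substitutions at Baseline and Post-Baseline in Epitope") and Listings 1.3-1.6 show all substitutions before and after treatment, emergent or not.

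**The concern.** The definition behind both primary endpoints should be executable as written, and this one is not. Section 8.2 names a baseline cut-off without saying what happens to a substitution that exceeds it. The reader has to supply the rule from section 10.

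Once the rule is supplied, a second matter appears. The baseline cut-off is 5% even when the post-baseline cut-off is 50%. A residue at 20% before treatment and 90% at Day 14 has become the consensus residue, but it is emergent at neither level. Protocol 6.2 gives possible selection of variants as the study's rationale, and a minority residue becoming the majority is one form that selection could take. The SAP describes no within-patient count of such cases.

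**Working it through.** **1. Inputs.** The cut-offs >5% and >50% come from SAP 8.2. Baseline and post-baseline frequencies each fall in one of three bands: none or <=5%, >5-50%, >50%.

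**2. Two readings.** Literal: baseline >5% and post-baseline above the cut-off. Intended: no record >5% at baseline, and post-baseline above the cut-off. The last column shows whether consensus status (>50%) changes.

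| Baseline to post-baseline | Literal: consensus / minority | Intended: consensus / minority | Consensus status |
|---|---|---|---|
| <=5 to <=5 | no / no | no / no | same |
| <=5 to >5-50 | no / no | no / yes | same |
| <=5 to >50 | no / no | yes / yes | gained |
| >5-50 to <=5 | no / no | no / no | same |
| >5-50 to >5-50 | no / yes | no / no | same |
| **>5-50 to >50** | yes / yes | **no / no** | **gained** |
| >50 to <=5 | no / no | no / no | lost |
| >50 to >5-50 | no / yes | no / no | lost |
| >50 to >50 | yes / yes | no / no | same |

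The literal reading counts unchanged substitutions and rejects new ones, so it cannot be what is meant. On the intended reading, two cells gain consensus status and one of them is left out. Two further cells lose consensus status; they also change the consensus sequence and are not counted as emergent.

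**3. Baseline depth.** Take a rise from 10% to 99%. If the baseline sample supports >5% calls, the 10% record is seen and the rise is not emergent. If the baseline supports consensus calls only, the 10% is not seen, and the same rise is counted as de novo. The protocol and SAP give no rule for this.

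**4. Possible size.** Let d be the proportion of patients with a de novo change and e the proportion with an enriched one. A patient may have both, so

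(de novo or enriched) - d lies between max(0, e - d) and min(e, 1 - d).

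The documents give no value for e and no planning rate at >50%. With assumed e of 1%, 2% and 5%, and d between 5% and 95%, the lower limit is 0 and the upper limit is e: 0-1, 0-2 and 0-5 percentage points.

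**5. Precision of an added row.** Protocol Table 2 uses the score interval with continuity correction (q = 1 - p, z = 1.96):

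- lower = [2np + z² - 1 - z√(z² - 2 - 1/n + 4p(nq + 1))] / [2(n + z²)]
- upper = [2np + z² + 1 + z√(z² + 2 - 1/n + 4p(nq - 1))] / [2(n + z²)]

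Check against the protocol, p = 0.09 and n = 500: lower = (92.84 - 25.25)/1007.68 = 6.7%; upper = (94.84 + 25.50)/1007.68 = 11.9%. This is the printed interval. The protocol's 50% of 400 example (45.0-55.0%) also reproduces.

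| Enriched patients | n | 95% CI |
|---|---|---|
| 0 | 400 | 0-1.2% |
| 4 (1%) | 400 | 0.3-2.7% |
| 0 | 100 | 0-4.6% |
| 1 (1%) | 100 | 0.1-6.2% |

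n = 400 is the protocol 8.5 example; n = 100 is an assumption. For a case with no events the lower limit is set to 0.

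**The case against.** **The literal reading is not the plan.** Section 8.2 calls its values thresholds, which fits calling cut-offs for the two record sets being compared, and section 10 requires comparison with baseline. This stands. A reader might infer that the analysis will reject new changes and count old ones. The documents do not support that; the literal result is a drafting fault.

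**A de novo rule is legitimate.** Protocol 8.3.2.1 speaks of changes that arise following treatment, and a substitution already at 20% did not arise afterwards. This stands as a reason to keep the de novo count as the main result. It does not settle the matter, because the endpoint is worded as any change from baseline and is reported at the consensus level, where the sequence has changed.

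**Secondary objective 5 adds little.** A reader might infer that the rule contradicts that objective. Protocol 7.2 limits it to changes "compared to baseline following sotrovimab administration for samples with viral loads below the threshold for detection of AA changes at >5% allelic frequency". Where the baseline sample is also below that threshold, a >5-50% baseline band cannot be observed. The point therefore rests on the primary endpoint.

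**The cases are visible.** Listings 1.3-1.6 are sorted by subject and visit, so an enriched case can be found by comparing the >5% and >50% listings. Protocol 8.5 also sends spike changes to the MHRA at patient level. This stands: no data are lost, only a count is missing.

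**Unseen sources.** The table shells and the laboratory manual were not available and may hold the derivation or a depth rule.

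**Conclusion.** The point holds in a limited form. The definition in SAP 8.2 lacks its operative condition and should be corrected. On the intended reading, a rise from >5-50% to >50% is the only gain of consensus status that no treatment-emergent table counts. Falls from >50% are not counted as emergent either.

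The effect on the primary results cannot be derived. It may be zero, because a patient with another new change is counted anyway. For that reason it probably matters more for the epitope than for the whole spike. The 0-1, 0-2 and 0-5 point ranges rest on assumed frequencies.

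Two stronger readings are not supported. The documents do not show that the interim counts are wrong, because they do not show which reading was programmed. Nor can it be said that the rule hides selection by sotrovimab: protocol 8.9 states that, without an untreated comparator, the design allows no meaningful inference about the association between treatment and new mutations.

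**What to change.** 1. Reword SAP 8.2 as a condition: a substitution is treatment-emergent if it has no record >5% at baseline and is >50% (consensus) or >5% (minority) post-baseline. Cross-refer section 10 to it.
2. Keep the de novo count as the main result. In the final consensus tables (spike 1.11 and 1.47, epitope 1.12), add a descriptive row with 95% CI, as in protocol 8.7.1, for patients with a substitution at >5-50% at baseline and >50% post-baseline. Add a combined de novo-or-enriched row. List both frequencies for each case, and label the rows as added after the interim analysis, with no attribution to sotrovimab.
3. Leave patients whose baseline supports consensus calls only in the de novo count, and footnote how many emergent cases have such a baseline, because enrichment cannot be ruled out for them. Take the denominator of the enriched row from patients whose baseline supports >5% calls. The combined row needs only to know that baseline was not >50%, so it can use the de novo denominator.

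**Cost.** A wording change, one flag from allele frequencies already held, and two extra rows per table. The rows are not fully pre-specified, because SAP 2.2 records the interim as done. Some cases will only drift across 50% (49% to 51%, say), which is why both frequencies are listed. If the interim used another reading of 8.2, its emergent counts would need rerunning.

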8.3.2. Outcome definitions

8.3.2.1. Primary Endpoint (Primary Objective)

1. Proportion of patients eligible for sequence analysis that have any AA change from baseline in the epitope of sotrovimab binding in samples collected at Day 7, 14 and 28 (+/-2 days) (Primary Objective 1)
2. Proportion of patients eligible for sequence analysis that have any AA change from baseline in the spike protein in samples collected at Day 7, 14 and 28 (+/-2 days) (Primary Objective 2)

Laboratory process

Samples will be dispatched by sites (baseline sample) and patients or HCPs if patients are hospitalised (follow-up samples) to a central analytical laboratory which will follow its own procedures for sequencing techniques.

Sequence analysis of the SARS-CoV-2 spike gene will be attempted on swab samples from all participants eligible for sequence analysis. Viral load will also be measured for all samples. Changes in the spike protein that arise following treatment will be determined by comparing baseline and post-baseline sequencing data for a given patient. More detailed information will be available in the overarching study laboratory manual.

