8.5. Study Size

The primary endpoints are the proportion of patients eligible for sequence analysis that have any AA change from baseline i) in the epitope of sotrovimab binding and ii) in the spike protein at Day 7, 14 and 28 (+/-2 days). The AA changes from baseline in the spike protein will be submitted to MHRA at the individual-patient level as part of ongoing surveillance reporting. Precision around the estimates of the primary endpoints will help to define the target sample size. No prior information about these precise endpoints is available, and the closest comparable available data are derived from the COMET-ICE clinical trial (i.e. conducted in immunocompetent patients with co-morbidities).

Preliminary analyses of these sequencing data reported:

- The percentage of sotrovimab treated patients that had treatment emergent AA changes detected **in the epitope of sotrovimab binding** at the consensus sequencing level was approximately 20% (when emergent changes were defined at 5% allelic frequency), and approximately 9% (when defined at 15% frequency)
- The percentage of sotrovimab treated patients that had emergent AA changes more broadly **across the spike protein** was approximately 80% and 52% (defined at 5% and 15% allelic frequency respectively).

A higher prevalence is expected in IC patients.

Precision calculations based on this information, and some additional values, are presented below (output from the software PASS (NCSS, LLC, Version 19.0.1). They show that, for example:

- If 50% of patients with AA changes that meet the criteria for the variable of interest (i.e. the estimated percentage that gives the widest confidence interval (CI)) is observed, then a sample size of 500 patients will give reasonable precision around the estimate (95% CI 45.5%-54.5%).
- If 9% of patients that meet the criteria is observed, a target sample size of 500 patients will also yield reasonable precision around the estimate (95% CI 6.7%-11.9%).

Table 2 Numerical Results for Two-Sided Confidence Intervals for One Proportion – Confidence Interval Formula: Score with Continuity Correction [Fleiss, 2003; Newcombe, 1998]

| Confidence Level | Sample Size (N) | Actual Width | Proportion (P) | Lower Limit | Upper Limit |
|------------------|-----------------|--------------|----------------|-------------|-------------|
| 0.950 | 500 | 0.041 | 0.050 | 0.033 | 0.074 |
| 0.950 | 500 | 0.052 | 0.090 | 0.067 | 0.119 |
| 0.950 | 500 | 0.055 | 0.100 | 0.076 | 0.131 |

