Listing	1.6	Listing of all Baseline and Post-baseline Epitope Substitutions – Consensus Sequence (Allelic frequency >50%)	Safety	Interim, Final
Listing	1.7	Listing of all Treatment-emergent Spike protein Amino Acid Substitutions – Minority species (Allelic frequency >5%)	Safety	Interim, Final
Listing	1.8	Listing of all Treatment-emergent Spike protein Amino Acid Substitutions – Consensus sequence (Allelic frequency >50%)	Safety	Interim, Final
Listing	1.9	Listing of all Treatment-emergent Epitope Amino Acid Substitutions – Minority species (Allelic frequency >5%)	Safety	Interim, Final
Listing	1.10	Listing of all Treatment-emergent Epitope Amino Acid Substitutions – Consensus sequence (Allelic frequency >50%)	Safety	Interim, Final
Listing	1.11	Listing of all Treatment-emergent Epitope Amino Acid Substitutions – Minority species (Allelic frequency >5%) by VOI/VUI	Safety	Interim
Listing	1.12	Listing of Variant of Concern/Under Investigation (VOC/VUI)	Safety	Interim, Final

This document is confidential.

Listing	1.131	Listing of Nasal/oropharyngeal swab SARS CoV2 Viral Load	Safety	Interim, Final
Listing	1.132	Listing of Nasal/oropharyngeal swab SARS CoV2 Viral Load for subjects with missing baseline viral load	Safety	Interim, Final
Listing	1.14	Listing of Nasal/oropharyngeal swab SARS CoV2 viral load by epitope substitution	Safety	Interim
Listing	1.15	Listings of Hospital Admission	Safety	Interim, Final
Listing	1.16	Listings of ICU Hospital Admissions	Safety	Interim, Final
Listing	1.17	Listings of requirement for Oxygen Support, Non-invasive, Invasive ventilation, ECMO	Safety	Interim, Final
Listing	1.18	Listings of Deaths	Safety	Interim, Final
Listing	1.19	Listings of All Adverse Events	Safety	Interim, Final
Listing	1.20	Listings of All Serious Adverse Events	Safety	Interim, Final
Listing	1.21	Listings of Hypersensitivity Adverse Reactions	Safety	Interim, Final
Listing	1.22	Listings of Anaphylactic Adverse Reactions	Safety	Interim, Final
Listing	1.23	Listings of All Serious Adverse Events	Safety	Interim, Final
		Additional Listings for Final Analysis		
Listing	1.24	Listings of All Protocol Deviations	Safety	Final
Listing	1.25	Listings of Medical History	Safety	Final
Listing	1.26	Listings of Prior and Concomitant Medications	Safety	Final
Listing	1.27	Listing of Nasal/oropharyngeal swab SARS CoV2 Viral Load of Participants Meeting Criteria for Viral Rebound	Safety	Final
Listing	1.28	Listing of All S Protein Substitutions (Allelic frequency >1%)	Safety	Final

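### For minority species, the SAP uses the same 5% cut at Day 0 and at follow-up with no minimum rise, so a substitution at about 3-5% on Day 0 can be counted as treatment-emergent through a trivial or chance rise

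*SAP*

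**What the plan says.** Protocol 8.3.2.1 sets the target: "Changes in the spike protein that arise following treatment will be determined by comparing baseline and post-baseline sequencing data for a given patient".

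SAP 8.2 (Key Definitions, Treatment Emergent) turns this into two rules:

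- Consensus: "Treatment emergence for consensus will include baseline records of allelic frequency" above 5%, with a post-baseline cut of 50%.
- Minority: "whereas treatment emergence for minority will include baseline records of allelic frequency" above 5%, with a post-baseline cut of 5%.

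The opening of SAP section 10 gives a second definition, under which a treatment-emergent substitution or change from baseline "is defined as any amino acid substitutions detected at post-baseline visits compared to baseline sequence". It adds no threshold, no minimum rise and no check below 5%.

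SAP 10.1 reports both primary endpoints at the two levels; results "will be presented separately for Minority species (>5% allelic frequency) as well as consensus sequence (>50% allelic frequency"). The minority results are in Tables 1.13 (spike), 1.14 (epitope) and 1.48 (spike, by subject), with Listings 1.7 and 1.9.

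The SAP's index of listings includes, for the final analysis, Listing 1.28: "Listing of All S Protein Substitutions (Allelic frequency >1"%). Calls between 1% and 5% will therefore be held, but no table or derivation is described as using them.

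**The concern.** The two rules treat Day 0 differently. The consensus rule looks back well below its own reporting level: a variant at 10% on Day 0 that reaches 60% is not called emergent, because it was already visible. The minority rule leaves no such margin. A Day 0 value just under 5% is treated as absence, and any later value just over 5% as emergence.

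At stake is the meaning of the >5% version of both primary endpoints. It can mix substitutions that were not seen on Day 0 with substitutions that were there at nearly the same frequency and crossed the line by a small rise or by measurement noise. The protocol (8.9, Role of Sotrovimab) acknowledges that there is no untreated comparator, so nothing in the design shows how large this background is.

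**Working it through.** **The plan's own figures.** The documents give no figure for the emergence rule. What can be reproduced is the precision in Protocol 8.5, Table 2. The score interval with continuity correction at N = 500 gives 6.7%-11.9% for 9% and 45.5%-54.5% for 50%, as printed. The other six rows also agree.

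**Model for a chance crossing.** Take one site whose true frequency f is the same at every visit, with N0 templates read on Day 0 and N1 at follow-up, and with counts binomial:

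P(false emergent) = P(X0/N0 ≤ 5%) × P(X1/N1 > 5%)

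The cuts come from SAP 8.2. N0, N1 and f are assumptions.

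Example with f = 4%, N0 = 1,000, N1 = 100: P(X0 ≤ 50) = 0.951, P(X1 ≥ 6) = 0.212, product 0.201. The reverse crossing (above 5%, then 5% or less) has probability 0.039.

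P(false emergent) per site for one follow-up sample, with N0 = 1,000:

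| True f | N1 = 1,000 | N1 = 500 | N1 = 100 | N1 = 50 |
|---|---|---|---|---|
| 1% | about 0 | about 0 | 0.05% | 1.4% |
| 2% | about 0 | about 0 | 1.5% | 7.8% |
| 3% | 0.02% | 0.55% | 8.1% | 18.9% |
| 4% | 4.7% | 10.2% | 20.1% | 30.7% |
| 5% | 24.9% | 24.0% | 20.6% | 24.7% |

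**Repeated samples.** If all three follow-up samples are sequenced, the chance is P(X0/N0 ≤ 5%) × [1 − P(X/N ≤ 5%)³]. At 500 templates throughout, this is 26% for f = 4% and 1.6% for f = 3%.

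**Amplification noise.** A beta-binomial model (500 at both visits, correlation 0.01) gives 0.8% at f = 1%, 4.3% at 2%, 11.3% at 3% and 19.5% at 4% for one follow-up sample.

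**Small real rise.** A true change from 4% to 6% is called emergent 54%, 71% and 86% of the time at 200, 500 and 1,000 templates at both visits.

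**Consensus.** For a site at 5%, the chance of a read above 50% is effectively zero at 100 or 500 templates.

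**Effect on a patient-level proportion.** If t is the true rate and q the share of the other patients falsely called, the reported rate is t + (1 − t)q. With t = 20% (the planning value for the epitope) and q = 5% (assumed), it is 0.20 + 0.80 × 0.05 = 24.0%. The 95% interval around 20% at N = 500 is 16.6%-23.8%. With q = 1% it is 20.8%. For spike, with t = 80% and q = 5%, it is 81.0%.

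**Would the >1% calls identify these cases?** With f constant at 3-5%, the share of false-emergent calls that also have a Day 0 call above 1% is 99.7-100% at 500 templates, 94-99.6% at 200 and 79-94% at 100. Under the beta-binomial model it is 85-97.5%.

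**The case against.** Several points on the other side are sound.

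- **Viral-load gate.** Secondary Objectives 4 and 5 confine >5% analysis to samples above the assay threshold and send lower-load samples to consensus reporting only. If the gate also governs the primary minority tables, it removes many of the low-template samples behind the largest figures. The threshold value is not given, so the lower end of the range may be the relevant one.
- **Expansion is of interest.** The rationale is selection of variants by antibody, and the endpoint is any change from baseline. Real growth of a 3% variant belongs in the study. It should still be distinguishable from a substitution not seen on Day 0, and a chance crossing is neither.
- **5% is the protocol's minority level**, and nothing states that calls above 1% are reliable. This rules out a new threshold, but not a supplementary split.
- **The study is descriptive** and the >50% results stand beside the >5% results. No test depends on the rule; a primary proportion does.

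Four stronger readings are tempting and are not supported:

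- That every variant at 1-5% on Day 0 is at risk. Chance matters at about 3-5%. At 1-2% it needs few templates or added noise.
- That false upward crossings outnumber downward ones in general. With 1,000 and 100 templates, a true 5% gives 20.6% up and 28.5% down, and a true 6% gives 5.6% up and 39.6% down. The narrower statement holds: where nothing has changed, only an upward crossing enters the count. Noise can also hide a real rise, so inflation is possible rather than certain.
- That the planning rates measure the error. For the epitope, Protocol 8.5 gives "approximately 20% (when emergent changes were defined at 5% allelic frequency), and approximately 9% (when defined at 15% frequency"), and for spike 80% against 52%. A reader might infer that 55% ((20 − 9)/20) and 35% ((80 − 52)/80) of positive patients are suspect. These rates come from another trial in immunocompetent patients and say nothing about Day 0 frequency: a change from 0% to 10% lies in the same gap.
- That a Day 0 call is strictly pre-treatment. Protocol Table 1 allows the swab during infusion or up to two hours after it.

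**Conclusion.** The point holds for minority species only. With both cuts at 5% and no minimum rise, a substitution at about 3-5% on Day 0 can enter the >5% primary proportions without a meaningful change. With 1,000 baseline templates and 1,000 down to 50 at follow-up, the chance per site is about 5% to 31% at a constant 4% and about 0.02% to 19% at a constant 3%. These are illustrations: template number, read depth, the assay threshold and the number of patients with 1-5% calls on Day 0 are not in the documents, so no corrected study proportion can be given. The epitope endpoint, with the lower expected rate, is the more sensitive of the two.

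The conclusion also rests on a reading of SAP 8.2. Taken literally, its minority sentence could mean that a Day 0 call above 5% is required, which would exclude every substitution absent on Day 0. The workable reading is that only Day 0 calls above 5% form the comparator. The SAP should say so.

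**What to change.** 1. In SAP 8.2, state how a Day 0 call at or below 5% is handled in the minority derivation, and align the definition at the start of section 10 with it.
2. Keep the >5% headline results unchanged.
3. Add to Tables 1.13, 1.14 and 1.48 a supplementary patient-level split from the calls behind Listing 1.28: patients with an emergent substitution that has no Day 0 call above 1%, and patients whose emergent substitutions all had a Day 0 call above 1% and up to 5%. If patients may instead appear in both rows, say so in a footnote.
4. Describe the second group as a rise in a variant already detected on Day 0, still relevant to selection, and not as newly arisen.

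The consensus tables (1.11, 1.12 and 1.47) need no change. The cost is a sentence or two of SAP text, one derived flag from data already planned for listing, and two rows in each of three tables. The downside is that the reliability of 1-5% calls is not stated: a spurious Day 0 call would move a genuinely new substitution into the second group. The split should therefore be labelled a sensitivity analysis and not a replacement threshold.
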